1. INTRODUCTION

Name of Sponsor

Curatek Pharmaceuticals, LLC

Active Ingredient(s) and Dose of Investigational Products

- BV Gel: 0.9% metronidazole gel (45 mg of metronidazole/5 grams of gel)
- VVC Gel: 0.8% terconazole gel (40 mg of terconazole/5 grams of gel)
- Combination Gel: 0.9% metronidazole gel and 0.8% terconazole gel (45 mg metronidazole and 40 mg of terconazole/5 grams of gel)

Protocol Number

MTC-001

This analysis plan describes the statistical techniques that will be used to assess the efficacy, safety, and tolerability of BV Gel, VVC Gel, and Combo Gel, in subjects diagnosed with bacterial vaginosis (BV), vulvovaginal candidiasis (VVC), or concurrent BV and VVC (Mixed Infection). The formats for the tables, listings, and figures described in this SAP are provided in a companion document.

The study has been conducted as Protocol MTC-001, finalized December 12, 2014 and amended on March 12, 2015. No subjects were enrolled under the protocol finalized on December 12, 2014 and there have been no previous statistical analysis plans.

1.1 Study Objectives

There are three primary objectives of the trial; one for each product/indication. They are to:

1. BV Study: Evaluate the safety and efficacy of BV Gel in the treatment of bacterial vaginosis (BV)
2. VVC Study: Evaluate the safety and efficacy of VVC Gel in the treatment of vulvovaginal candidiasis (VVC)
3. Mixed Infection Study: Evaluate the safety and efficacy of Combo Gel in the treatment of concurrent BV and VVC (mixed infections)

1.2 Study Design

This is a multi-center, phase III trial, comprised of three studies, each designed to test the safety and efficacy of a different investigational product, for a specific vaginal infection/indication. They are:

1. Bacterial Vaginosis (BV) Study: A randomized, double-blind, parallel-group, placebo-controlled study to test the safety and efficacy of BV Gel (0.9% metronidazole gel) for the treatment of BV
2. Vulvovaginal Candidiasis (VVC) Study: A randomized, double-blind, parallel-group, placebo-controlled study to test the safety and efficacy of VVC Gel (0.8% terconazole gel) for the treatment of VVC
3. Mixed Infection (Concurrent BV and VVC) Study: A randomized, double-blind, parallel-group, active-controlled study to test the safety and efficacy of Combo Gel (0.9% metronidazole gel and 0.8% terconazole gel) for the treatment of Mixed Infection

All study medication is intravaginal and will be dosed as one applicator for three consecutive days. Subjects who sign an informed consent form (ICF), are diagnosed with BV, VVC, or Mixed Infection, and meet eligibility requirements will be enrolled into the appropriate infection study and subsequently

randomized to treatment based on clinical diagnosis at the screening and enrollment/baseline visit (Visit 1). BV subjects will be entered into the BV Study, VVC subjects will be entered into the VVC Study, and concurrent BV and VVC (Mixed Infection) subjects will be entered into the Mixed Infection Study.

All subjects will be asked to return for a test of cure visit (Visit 2) 7-14 days after randomization. If a subject is menstruating on the day of the scheduled visit, she should be rescheduled to return 24 hours after completion of menses. Subjects who in the opinion of the investigator/clinician require additional treatment for vaginal discomfort/symptoms and subjects who self-medicated for vaginal discomfort/symptoms, will be terminated from the study. All other subjects will return for a follow-up evaluation visit (Visit 3) 21-30 days after randomization.

Study procedures will be identical in all three infection studies with the exception of safety labs (i.e. Hematology: complete blood count (CBC) with differential and Chemistry: blood urea nitrogen (BUN), Creatinine, alanine aminotransferase (ALT), aspartate aminotransferase (AST), alkaline phosphatase (ALP), and bilirubin), which will only be obtained at Visit 1 and Visit 2 on subjects entered into the Mixed Infection Study. There will be one case report form (CRF) for each subject. The CRF will be the same for all three infection studies. Analysis of safety and efficacy will be performed separately for each investigational product.

All eligible subjects will be randomized at the baseline visit (Visit 1) utilizing an interactive voice response (IVR)/interactive web response (IWR) system. Subjects in the BV or VVC study will be randomly assigned to one of two treatment groups in a 1:1 ratio while subjects in the Mixed Infection study will be randomized to one of three treatment groups in a 1:1:1 ratio. All treatments, regardless of study, consist of three doses, to be administered by vaginal applicator at bedtime for three consecutive days.

Subjects will be randomized to treatment as follows:

- Subjects diagnosed with BV will be randomized to receive treatment with either BV Gel (0.9% metronidazole gel) or Placebo Gel. Each 5-gram dose of BV Gel contains 45 mg of metronidazole for a total dose of 135 mg of metronidazole.
- Subjects diagnosed with VVC will be randomized to receive treatment with either VVC Gel (0.8% terconazole) or Placebo Gel. Each 5-gram dose of VVC Gel contains 40 mg of terconazole for a total dose of 120 mg of terconazole.
- Subjects diagnosed with Mixed Infection will be randomized to receive treatment with BV Gel, VVC Gel, or Combo Gel (0.9% metronidazole and 0.8% terconazole). Each 5-gram dose of the Combo Gel contains 45 mg of metronidazole and 40 mg of terconazole for a total dose of 135 mg of metronidazole and 120 mg of terconazole.

The study consists of three visits: a Screening and Enrollment/Baseline visit (visit 1), a Test of Cure visit (visit 2) and one follow-up clinic visit (visit 3). Visit 2 will occur 7-14 days after randomization for the purpose of determining subject compliance/evaluability with drug administration and study instructions, evaluating the subject's response to therapy and whether or not additional treatment is needed (i.e. cure or failure), and obtaining information on concomitant medication use and possible adverse events. Visit 3 will occur 21-30 days after randomization for the purpose of determining subject compliance; determining either presence or absence of the subject's baseline infection and whether or not additional treatment is needed; and obtaining information on concomitant medication use and possible adverse events.

If a subject was unable to return for Visit 2 but returns for Visit 3, available information that was to be obtained at Visit 2 regarding study drug administration/compliance and time to resolution/reoccurrence of symptoms may be obtained at Visit 3. The subject's diary should be reviewed and unused drug collected. Subjects in the Mixed Infection Study who missed Visit 2 should have hematology and chemistry labs obtained at Visit 3.

2. CHANGES IN THE CONDUCT OF THE STUDY OR PLANNED ANALYSES

2.1 Changes in the Conduct of the Study

The original protocol was version 1.0 and dated December 12, 2014. There has been one revision to the protocol, numbered version 2.0 and dated March 12, 2015, as of the development of this Statistical Analysis Plan (SAP). Changes per the revision are incorporated in this SAP.

2.2 Changes from the Analyses Planned in the Protocol

This analysis plan details analyses to be conducted for the study. Some of the analyses detailed here may be more explicit or in some aspects different than those stated in the protocol. In case of differences, this SAP supersedes the statistical sections in the protocol.

3. STUDY OBSERVATIONS

The evaluation of subject eligibility will occur at the Baseline visit (visit 1). Eligible subjects will receive a maximum duration of treatment of three days and a maximum trial duration of 30 days from the time of randomization. The test of cure visit (visit 2) will occur 7-14 days after randomization. If the subject did not need additional treatment for vaginal discomfort/symptoms (and the subject did not self-medicate), the subject will be asked to return 21-30 days after randomization (visit 3).

3.1 Screening/Baseline Evaluations

Baseline (visit 1) medical evaluations will include:

- Medical and surgical history
- Contraceptive/obstetric status and gynecologic history
- Use of concomitant medications (i.e. current and within 30 days of enrollment) as well as treatments for BV and/or VVC infections within the past year
- Subject Assessment of Symptoms: Subjects will be asked to rate their current vulvovaginal symptoms of itching, burning, and irritation as absent=0, mild=1, moderate=2 or severe=3. The sum of the symptom score will be added to the vulvovaginal signs score obtained during the pelvic examination to determine a combined symptom and sign severity score.
- General physical examination and vital signs
- Laboratory tests
 - Urine pregnancy test for all women of child bearing potential
 - Papanicolaou smear (if subject is ≥ 21 years old and a Pap smear was not done within the past 3 years)
 - Tests for *Neisseria gonorrhoeae*, *Chlamydia trachomatis*, and *Trichomonas vaginalis*
 - Culture for *Herpes simplex* (only if suspected)
 - Vaginal culture for *Candida* species
 - Vaginal Gram stain

- CBC with differential and blood chemistries (i.e. BUN, Creatinine, ALT, AST, ALP, and bilirubin) for subjects enrolled in the Mixed Infection Study

Baseline (visit 1) pelvic examination and specimen collections will include:

- Visual inspection: rule out lesions caused by Herpes simplex virus or human papilloma virus (i.e. genital warts)
- Vulvovaginal signs rating: rate the degree of vulvovaginal edema, erythema, and excoriation as absent = 0, mild = 1, moderate = 2 or severe = 3. The sum of these ratings will be added to the vulvovaginal symptoms score given by the subject to determine a combined symptom and sign severity score. This total score must be > 2 in order to meet entry criteria for enrollment into the VVC or Mixed Infection study.
- Vaginal discharge characterization: By visual examination, characterize vaginal discharge in accordance with the descriptions below.
 - Normal/physiologic: normal discharge may vary in appearance and consistency depending on the menstrual cycle;
 - Abnormal: consistent with BV (i.e. off-white [milky or gray], thin, homogeneous discharge);
 - Abnormal: consistent with VVC (i.e. white, creamy, and curdy [cottage cheese like] adherent to the epithelium);
 - Abnormal: consistent with Mixed Infection (i.e. discharge of varying characteristics with relation to odor, color, and consistency)
- pH measurement: Obtain a vaginal pH measurement with the pH indicator strips provided.
- KOH Whiff Test
- KOH and saline wet mounts
- Vaginal Candida culture: Obtain a Candida culture as specified in the central laboratory manual utilizing the collection and shipment supplies provided.
- Vaginal Gram Stain: Obtain a Gram Stain as specified in the central laboratory manual utilizing the collection and shipment supplies provided.
- Papanicolaou smear: Obtain a Pap smear if subject is ≥ 21 years old and has not had one within the past 3 years.
- Test for Neisseria gonorrhoeae, Chlamydia trachomatis, and Trichomonas vaginalis as specified in the central laboratory manual utilizing the collection and shipment supplies provided.
- Culture for Herpes simplex (only if suspected).

3.2 Test of Cure Visit (Visit 2) Evaluations

The procedures listed below will be performed 7-14 days after randomization for the purpose of determining subject compliance/evaluability with drug administration and study instructions, evaluating the subject's response to therapy and whether or not additional treatment is needed (i.e. cure or failure), and obtaining information on concomitant medication use and possible adverse events.

- Review of Diary
- Assessment of Compliance: Subjects are queried to determine compliance with study drug administration and study instructions.
- Time to Symptom Resolution/Reoccurrence: Symptom resolution and reoccurrence will be assessed by review of the subject's diary and subject interview. Dates of symptom resolution and/or symptom recurrence should be documented.
- Subject Assessment of Symptoms: Subjects will be asked to rate their current vulvovaginal symptoms of itching, burning, and irritation as absent=0, mild=1, moderate=2, or severe=3. The sum of this symptom score will be added to the vulvovaginal signs score obtained during the pelvic examination to determine a combined symptom and sign severity score.
- Laboratory Tests and Specimen Collections: The lab tests listed below will be obtained at Visit 2.

- CBC with differential and blood chemistries (i.e. BUN, Creatinine, ALT, AST, ALP, and bilirubin) only for subjects enrolled in the Mixed Infection Study
- Vaginal culture for Candida species
- Vaginal Gram stain
- Pelvic Examination and Specimen Collections
 - Vulvovaginal signs rating
 - Vaginal discharge characterization
 - Vaginal pH measurement
 - KOH Whiff Test
 - Saline wet mount
 - Vaginal Candida culture
 - Vaginal Gram stain
- Assessment of Clinical Status, Need for Additional Treatment: Following subject evaluation, the investigator/clinician will be asked to document whether the subject requires any additional treatment for vaginal discomfort/symptoms. Subjects who do require additional treatment should be treated per investigator/clinician judgment and terminated from the study. Subjects who do not require treatment (and subjects who did not self-medicate) may remain in the study and return for their regularly scheduled follow up visit (Visit 3).
- Determination of Cure or Failure of Subject's Enrolled Infection:
 - BV subjects must satisfy all three of the clinical criteria listed below in order to be considered a BV cure (i.e. clinical cure).
 - Discharge has returned to normal/physiologic¹
 - The whiff test is negative for any amine "fishy" odor.
 - The saline wet mount is < 20% clue cells.

If in the investigator/clinician's opinion the subject requires additional treatment for BV or if the subject self-administered drug therapy for vaginal discomfort/symptoms after completing therapy, the subject will be considered a BV failure².

 - VVC subjects must have all signs and symptoms attributable to VVC resolved (i.e. clinical cure), in order to be considered a VVC cure. If in the investigator/clinician's opinion the subject requires additional treatment for VVC or if the subject self-administered drug therapy for vaginal discomfort/symptoms after completing therapy, the subject will be considered a VVC failure².
 - A Mixed Infection cure is a subject who meets the definition of a BV cure AND a VVC cure. If in the investigator/clinician's opinion the subject requires additional treatment for either BV, VVC, or Mixed Infection or if the subject self-administered drug therapy for vaginal discomfort/symptoms after completing therapy, the subject will be considered a Mixed Infection failure.

1. In the event a subject treated for BV gets a secondary yeast infection following treatment and discharge is consistent with VVC (i.e. white, creamy, and curdy [cottage cheese like] adherent to the epithelium), the subject will be considered a clinical cure providing all other clinical criteria for BV cure are met and the subject has a positive yeast culture.

2. Self-administration of therapy includes prescription and OTC antimicrobial, anti-fungal, analgesics, or steroid treatments.

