4.2 Analysis Populations

The primary assessments of efficacy will be based on the modified intent-to-treat (mITT) population. In addition to the mITT analyses of the data, analyses will also be conducted on the per protocol (PP) population. The data analysis populations are defined as:

- ITT: The intent-to-treat population will include all subjects randomized to treatment.
- mITT: The modified intent-to-treat population will include all subjects randomized to treatment and administered at least one dose of study drug. Subjects who are Lost to Follow-up and for whom there is no documentation to ascertain whether or not they were administered treatment will be excluded from the mITT population.
 - In addition, to be included in the mITT population subjects in the VVC and Mixed Infection studies must have a positive baseline vaginal fungal culture for *Candida* species. Subjects in the BV and Mixed Infection studies must have a Gram stain Nugent score of ≥ 4 at the baseline visit.
 - Subjects randomized to treatment but whose baseline laboratory tests subsequently reveal positive results for *Trichomonas vaginalis*, *Chlamydia trachomatis*, and/or *Neisseria gonorrhoeae* will be excluded from the mITT population.
- PP: The per protocol population will include the subset of mITT subjects that had no major protocol violations and who are classified as efficacy evaluable with no missing data required to determine primary endpoints. Major protocol violations likely to bias assessment of the primary endpoint for the per protocol population will be determined prior to unblinding the data.
- Safety: The safety population will include all subjects randomized to treatment and administered at least one dose of study drug.

Major protocol deviations (i.e. deviations likely to bias assessment of the primary efficacy measure) that will be used to assess inclusion in the PP population will be determined and reviewed by the Sponsor prior to unblinding the data.

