4.3 Efficacy Endpoints and Evaluations

The primary and secondary endpoints are reflective of each of the infection studies within the protocol. These include:

Primary Endpoints

- BV Study: BV cure rate, with cure defined as normal/physiologic discharge, negative whiff test, and < 20% clue cells (i.e. clinical cure)
- VVC Study: VVC cure rate, with cure defined as resolution of all signs and symptoms attributable to VVC (i.e. clinical cure)
- Mixed Infection Study: Mixed Infection cure rate, with cure defined as BV cure (i.e. BV clinical cure) AND a VVC cure (i.e. VVC clinical cure)

Primary efficacy endpoint evaluations will occur at the test-of-cure Visit 2.

If a subject requires additional treatment for vaginal discomfort/symptoms (i.e. a BV subject requiring treatment for BV, a VVC subject requiring treatment for VVC or a Mixed Infection subject requiring treatment for BV and/or VVC) prior to or at Visit 2, the subject will be considered a treatment failure. These subjects will be evaluable for the modified intent-to-treat (mITT) and the per-protocol (PP) population analyses, providing all other evaluability criteria for these population groups have been met.

Additionally, if a subject self-medicates herself for vaginal discomfort/symptoms at any time prior to Visit 2, the subject will be considered a treatment failure. If this occurs, the subject will remain evaluable for the mITT analyses but will be non-evaluable for the PP analysis.

Secondary Endpoints

Note, for BV a Gram stain Nugent score cure will be defined as a score of < 4, i.e. 0 – 3.

- BV Study: BV clinical and Gram stain Nugent score combined cure rate, and Gram stain Nugent score cure rate alone; changes/improvements in Amsel criteria and Nugent scores; time to resolution of symptoms
 - In addition, cure rates over time will be explored
- VVC Study: VVC clinical and mycologic cure rates combined and mycologic cure alone; changes/improvements in signs and symptoms scores; eradication (or persistence) of individual fungal species; time to resolution of symptoms
- Mixed Infection Study: BV clinical and Gram stain Nugent score cure rates alone and combined; changes/improvements in Amsel criteria and Nugent scores; VVC clinical and mycologic cure rates alone and combined; changes/improvements in signs and symptoms scores; eradication or persistence of individual fungal species; time to resolution of symptoms

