14.2 Efficacy Summaries

Table 14.2.1.1	Summary of Primary Endpoint for BV Study – Test-of-Cure, mITT Population
Table 14.2.1.2	Summary of Primary Endpoint for BV Study – Test-of-Cure, PP Population
Table 14.2.2.1	Summary of Primary Endpoint for VVC Study – Test-of-Cure, mITT Population
Table 14.2.2.2	Summary of Primary Endpoint for VVC Study – Test-of-Cure, PP Population
Table 14.2.3.1	Summary of Primary Endpoint for Mixed Infection Study – Test-of-Cure, mITT Population
Table 14.2.3.2	Summary of Primary Endpoint for Mixed Infection Study – Test-of-Cure, PP Population
Table 14.2.4	Exploratory Analysis of Primary Endpoint by Month of Study, For Patients Receiving BV Gel – Test-of-Cure, mITT Population
Figure 14.2.5	Time Plot of Primary Endpoint by Month of Study, For Patients Receiving BV Gel – Test-of-Cure, mITT Population
Table 14.2.6	Summary of Visit 2 Symptom and Sign Severity Score, mITT Population
Table 14.2.7	Summary of Visit 2 Pelvic Exam, mITT Population
Table 14.2.8	Summary of Visit 2 Compliance Assessment, mITT Population
Table 14.2.9	Summary of Visit 2 Need for Additional Treatment, mITT Population
Table 14.2.10.1	Summary of Visit 2 BV Clinical Cure, mITT Population
Table 14.2.10.2	Summary of Visit 2 BV Clinical Cure, PP Population
Table 14.2.11.1	Summary of Visit 2 VVC Clinical Cure, mITT Population
Table 14.2.11.2	Summary of Visit 2 VVC Clinical Cure, PP Population
Table 14.2.12.1	Summary of Visit 2 Gram Stain Cure, mITT Population
Table 14.2.12.2	Summary of Visit 2 Gram Stain Cure, PP Population
Table 14.2.13.1	Summary of Visit 2 Candida Culture Cure, mITT Population
Table 14.2.13.2	Summary of Visit 2 Candida Culture Cure, PP Population
Table 14.2.14.1	Summary of Visit 2 Combined BV Clinical and Gram Stain Cure, mITT Population
Table 14.2.14.2	Summary of Visit 2 Combined BV Clinical and Gram Stain Cure, PP Population
Table 14.2.15.1	Summary of Visit 2 VVC Clinical and Candida Culture Cure, mITT Population
Table 14.2.15.2	Summary of Visit 2 VVC Clinical and Candida Culture Cure, PP Population

Table 14.2.16	Summary of Visit 2 Change in Pelvic Exam Results, mITT Population
Table 14.2.17	Summary of Visit 2 Change in Signs and Symptoms, mITT Population
Table 14.2.18	Summary of Visit 2 Eradication/Persistence of Candida Species, mITT Population
Table 14.2.19	Summary of Time to Resolution of Symptoms, mITT Population
Figure 14.2.20	Kaplan-Meier Curve of Time to Resolution of Symptoms

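### In the Mixed Infection Study, yeast discharge persisting from baseline can by itself make a subject a BV clinical failure, so the secondary BV clinical comparisons are likely to favour Combo Gel over BV Gel

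*SAP*

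**What the plan says.** SAP Section 3.2 makes BV clinical cure depend on three criteria, all of which must be met: discharge ("Discharge has returned to normal/physiologic"), a negative whiff test, and under 20% clue cells on the saline wet mount. Footnote 1 gives the only relief from the discharge criterion. It begins "In the event a subject treated for BV gets a secondary yeast infection following treatment and discharge is consistent with VVC". Such a subject still counts as cured of BV if she satisfies the remaining BV criteria and yeast grows on culture.

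The Mixed Infection Study reuses this definition: "A Mixed Infection cure is a subject who meets the definition of a BV cure AND a VVC cure". Section 4.2 requires for the mITT population that "subjects in the VVC and Mixed Infection studies must have a positive baseline vaginal fungal culture for *Candida* species". Section 1.2 lists the Mixed arms as BV Gel (metronidazole only), VVC Gel (terconazole only) and Combo Gel (both).

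The secondary endpoints in Section 4.3 include "Mixed Infection Study: BV clinical and Gram stain Nugent score cure rates alone and combined". Section 14.2 lists the matching outputs, such as Table 14.2.10.1, "Summary of Visit 2 BV Clinical Cure, mITT Population", and Tables 14.2.14.1 and 14.2.14.2 for clinical and Gram stain cure combined. Section 4.7.2 compares such binary outcomes between arms with a test and a 95% confidence interval for the difference.

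**The concern.** Footnote 1 accepts that yeast discharge should not turn a BV cure into a BV failure. As worded, it covers only yeast acquired after treatment. That leaves out the Mixed Infection Study, where every mITT subject has yeast at baseline and the arms differ in whether it is treated.

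Take two subjects with the same Visit 2 findings: negative whiff test, under 20% clue cells, VVC-type discharge and a positive yeast culture. In the BV Study, with newly acquired yeast, the subject is a BV clinical cure. In the Mixed Infection Study, with yeast persisting from baseline, she is a BV clinical failure. The second situation should be commoner on BV Gel than on Combo Gel. A Combo Gel advantage on BV clinical cure could therefore reflect terconazole clearing the discharge and not a better effect on BV.

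**Working it through.** **Reading the rule**

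1. Failing the discharge criterion alone means no BV clinical cure (Section 3.2).
2. The exception needs a yeast infection that is secondary and follows treatment (Section 3.2, footnote 1).
3. Mixed mITT subjects are *Candida*-positive before treatment (Section 4.2), so yeast persisting from baseline does not meet step 2.
4. The Mixed arms differ in antifungal content (Section 1.2), so the frequency of such discharge should differ by arm.
5. The resulting endpoint is formally compared between arms (Sections 4.3 and 4.7.2).

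**The plan's own figures**

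No stated figure is in dispute. Exact power of Fisher's test at the Section 4.5 rates is 90.6% (58 per arm, 0.50 vs 0.20), 99.94% (50 per arm, 0.70 vs 0.20) and 90.6% for each Mixed comparison (63 per arm, 0.35 vs 0.10). These agree with the plan to within rounding, and 58×2 + 50×2 + 63×3 = 405.

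**Illustrating the size**

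Inputs:
- True BV cure is 0.50 in both BV Gel and Combo Gel (Section 4.5 rate for BV Gel in the BV Study; equality is assumed).
- VVC clinical non-cure is 1 − 0.20 = 0.80 on BV Gel and 1 − 0.70 = 0.30 on Combo Gel. These are complements of the Section 4.5 clinical cure rates in the VVC Study, carried over by assumption. They are not rates of positive culture.
- BV and VVC outcomes are independent (assumed). The plan's Mixed rates for these arms fit this: 0.50×0.70 = 0.35 and 0.50×0.20 = 0.10.
- d is the share of VVC-uncured subjects with VVC-type discharge at Visit 2. The SAP gives no value, so a range is shown.

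Observed BV clinical cure is 0.50×(1 − 0.80d) on BV Gel and 0.50×(1 − 0.30d) on Combo Gel. The difference is 0.50×(0.80 − 0.30)×d = 0.25d, although true BV cure is equal.

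The last two columns give the chance, at 63 per arm and two-sided 0.05, that Combo Gel tests significantly better than BV Gel.

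| d | BV Gel | Combo Gel | Spurious difference (points) | Chi-squared | Continuity-corrected |
|---|---|---|---|---|---|
| 0 | 50.0% | 50.0% | 0 | 2.9% | 2.0% |
| 0.25 | 40.0% | 46.25% | 6.25 | 11.7% | 8.6% |
| 0.50 | 30.0% | 42.5% | 12.5 | 31.6% | 25.1% |
| 0.75 | 20.0% | 38.75% | 18.75 | 64.7% | 56.4% |
| 1 | 10.0% | 35.0% | 25 | 93.6% | 90.6% |

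At d = 1 the observed BV clinical rates equal the assumed Mixed cure rates (0.10 and 0.35): in this model the BV endpoint then carries no information separate from the Mixed cure.

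The ranges in Section 4.5 (BV Gel 0.45–0.55, VVC Gel 0.65–0.75, placebo 0.15–0.25) move the multiplier from 0.45×(0.65 − 0.25) = 0.18 to 0.55×(0.75 − 0.15) = 0.33, so the spurious difference lies between 18d and 33d points.

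**The case against.** Several counter-arguments have weight.

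- **The endpoint is secondary.** The only superiority claim in the Mixed Infection Study rests on Mixed cure (Sections 4.1 and 4.7.1). The SAP does not say that BV clinical cure there is meant to establish the contribution of a component. This stands and limits the importance of the point.
- **Readouts free of the problem are already planned.** Nugent cure alone is a listed secondary endpoint (Tables 14.2.12.1 and 14.2.12.2), and changes in Amsel criteria are also listed. A difference driven by discharge should show as a contrast with Nugent cure. This also stands, but the BV clinical and combined endpoints are still tested as defined.
- **Footnote 1 might be applied loosely.** A Mixed subject could be regarded as treated for BV. But a yeast infection present at baseline is not one she gets after treatment. If both readings are possible, the derivation needs settling before unblinding.
- **The numbers are soft.** One mild residual symptom is enough for VVC clinical non-cure, so 80% and 30% are not yeast persistence; d has no source in the SAP and independence is assumed. This stands: the direction is well supported, the size is not.

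A reader might go further and infer that the primary Mixed result is biased too. The document does not support that. VVC cure requires all signs and symptoms attributable to VVC to have resolved, so a subject with persisting VVC-type discharge would normally fail that component as well. The SAP does not spell this out: the scored signs are edema, erythema and excoriation, with discharge characterised separately (Section 3.1). Hence the primary is best called essentially unaffected, not wholly immune.

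**Conclusion.** The point holds as a minor one about secondary endpoints. Read literally, the BV cure rule counts VVC-type discharge persisting from the baseline infection against BV clinical cure in the Mixed Infection Study. Because only one of the two metronidazole arms contains an antifungal, BV clinical cure and BV clinical plus Nugent cure are likely to favour Combo Gel over BV Gel for a reason unrelated to BV. Nugent cure alone is not affected.

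The size is not known from the SAP. The 6 to 19 points for d between 0.25 and 0.75 are hypothetical: they need equal true BV cure of 50%, VVC clinical non-cure carried over from the single-infection study, and independence. A reader might take them as an estimate of the actual bias, but nothing in the SAP supplies d. They were also worked out for BV clinical cure only; the combined endpoint shares the mechanism, but its size was not calculated.

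**What to change.** Before unblinding, do one of the following for the Mixed Infection Study's secondary BV clinical endpoints.

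- **Preferred:** add an analysis, identical in all three arms, that defines BV cure by negative whiff test and under 20% clue cells without the discharge criterion, both with and without Nugent score below 4. Interpret any Combo Gel versus BV Gel difference in BV clinical cure alongside it and Nugent cure alone.
- **Alternative:** state that footnote 1 also applies, in all three arms, to yeast-type discharge persisting from baseline with a positive Visit 2 culture. This is weaker. It relaxes the definition mostly in the BV Gel arm, where it could excuse BV-related discharge masked by yeast. As worded it also misses discharge classed as consistent with Mixed Infection, a separate category in Section 3.1.

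Leave the primary Mixed cure unchanged.

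The cost is a sentence in the SAP, a derivation flag and one more table; discharge category, whiff test, wet mount, culture and Gram stain are all collected at Visit 2. The downside of the preferred option is a BV readout that ignores any genuinely BV-related discharge, which is why it supplements the defined endpoint. Neither option changes the rule that self-medication for vaginal symptoms counts as failure, a route by which untreated yeast could still lower the BV Gel rate.
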